This is a multiple institute study coordinated by Roswell Park Cancer Institute Network Office. See Appendix 2 for Network specific information.

Women will present to the University of Chicago Medical Center (UCMC) Breast Center and Roswell Park Cancer Institute (RPCI) breast center with either an abnormal mammogram, new discrete breast mass, or biopsy proven cancer. Those women with abnormal mammograms (BRIRADS 4 and 5) or suspicious masses will undergo a diagnostic core biopsy after being evaluated in the breast center, the intake point of all new breast cases through the surgical clinic. Once an invasive carcinoma is confirmed on core biopsy by our staff pathologist, the majority of women will undergo definitive surgery to remove the tumor and determine staging. Typically, at University of Chicago and RPCI the interval between biopsy and definitive surgery is between two-four weeks. To examine the interaction between ER α and P53 with and without tamoxifen unfixed tumor tissue (fresh or frozen) is needed. A pilot randomized trial is proposed in ER α positive women to study this interaction. ER α positive disease will be identified at their initial visit, or upon return to the clinic to discuss core biopsy results. A p53 staining will be performed on the diagnostic core biopsy if an ER α positive malignancy is identified (Allred score of 3 or higher). The results of the p53 status will not be used for eligibility. ER/PR/HER-2 analysis of the diagnostic core biopsy tissue is done routinely as a standard of care. Women with tumors which are ER α positive will be enrolled if they meet eligibility criteria. Women will either be randomized to standard of care surgical therapy or a four week intervention prior to surgery; Based on our preclinical studies four weeks of tamoxifen exposure is adequate to study the interaction between ER α , p53 and tamoxifen in the tumor tissue. During the intervention, blood will be drawn from the participants to measure levels of tamoxifen metabolites in the blood and test for polymorphisms that may decrease levels of active metabolites. Estradiol and estrone levels in the blood and tumor tissues of all patients with or without intervention will be measured.

Eligibility Criteria:

Inclusion Criteria:

- (a) The patient must consent to be in the study and must have signed an approved consent form conforming to institutional guidelines
- (b) The patient must be 18 years or older.

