- (c) Core biopsy should definitively demonstrate invasive carcinoma.
- (d) Invasive carcinoma should be ER α receptor positive
- (e) The tumor should be approximately at least 1 cm, to account for variability in imaging and imaging occult disease (physical exam, mammography, ultrasound). We recognize that from time to time because of this variation, there might

not be enough tissue available for analysis after surgical excision but this will allow the greatest opportunity to capture as many eligible patients as possible.

- (f) Patients in whom surgical excision of the tumor is part of standard of care management
- (g) ECOG score of 0 or 1
- (h) Negative serum or urine β -hCG pregnancy test at screening for patients of child-bearing potential (this is routinely done if the patient is premenopausal and having surgery)
- (i) Consent to participate in DBBR (RPCI only)

Exclusion Criteria:

- (a) Male patients are not eligible for this study
- (b) Female patients with inoperable tumors or women with stage 4 disease diagnosed on CT, PET, PET/CT or bone scan.
- (c) Patients with diagnosis by FNA cytology only
- (d) Pregnant or lactating women
- (e) Prior therapy for breast cancer, including irradiation, chemo- immuno- and/or hormonal therapy
- (f) Patients receiving any hormonal therapy, e.g. ovarian hormonal replacement therapy, infertility medications etc., are not eligible
- (g) Nonmalignant systemic disease (cardiovascular, renal, hepatic, etc.) that would preclude the patient from being subjected to surgical excision
- (h) Psychiatric or addictive disorders that would preclude obtaining informed consent
- (i) Patients known or suspected to have hypercoagulable syndrome or with history of venous or arterial thrombosis, stroke, TIA, or pulmonary embolism
- (j) Women with non-invasive disease or microinvasion are not eligible.
- (k) Women undergoing neoadjuvant chemotherapy are not eligible
- (l) women currently on tamoxifen and raloxifene for prevention are not eligible
- (m) Patients shall not receive any herbal/alternative therapies such as flaxseed or soy products or black cohosh.
- (n) Patients with a known mutation in p53 (Li Fraumeni Syndrome)

Unevaluable patients are defined as patients who do not have enough tissue for study or who come off early on tamoxifen, and will be replaced on study.

IV. TREATMENT PLAN AND RESEARCH METHODS:

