Patient would undergo standard of care surgical excision at completion of four week course of tamoxifen. We do not anticipate the four week therapy with tamoxifen to modify the surgical planning including type of breast surgery, sentinel node biopsy or to affect the clinical outcome. After completion of surgical excision they would be recommended routine adjuvant therapy including adjuvant chemotherapy, radiation therapy and at least 5 years of endocrine therapy as dictated by the patient's final stage.

This protocol does not prohibit patients enrolling in any other future investigational studies after completion of surgical excisions.

Dose Modifications And Delays

There will be no dose modification of tamoxifen therapy. The toxicity profile of four weeks of tamoxifen is unknown. In the event of any Grade 2 or higher toxicity during the study attributed to tamoxifen, it will be discontinued and patient will be permanently taken off the study.

VII. NONPROTOCOL THERAPY

Patients should not receive any cancer therapy other than that specified in the protocol or while on Tamoxifen.

Sex Hormonal Therapy

Patients should not receive any sex hormonal therapy such as birth-control pills, hormone replacement therapy or infertility medications while on this protocol.

Radiation Therapy

Patients may not receive any radiation therapy until the completion of the protocol therapy.

Anti-Hormonal therapy

Patients may not receive any hormonal therapy including Aromatase inhibitors or Raloxifene while on the protocol therapy. Patients should be off of these medications for at least 30 days prior to enrollment. They may receive the appropriate adjuvant therapy after surgery.

Alternative therapy

Patient shall not receive any herbal/alternative therapies such as flaxseed or soy products or other medications such as black cohosh.

Non-cancer therapy

Patient may continue all the therapies intended for other than cancer. Patients shall discuss the safety of receiving the concurrent non-cancer medications with the study investigator. If patients are on SSRI's they are not eligible.

VIII. PHARMACEUTICAL INFORMATIONTamoxifen [NSC#180973]

Tamoxifen is supplied in tablet form, each containing 20 mg.

Clinical Safety and Adverse Effects

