Adverse effects include hot flashes, nausea (vomiting is rare), vaginal bleeding, discharge or dryness, menstrual irregularities, and skin rash. Other rarely seen adverse effects are hypercalcemia, peripheral edema, leucopenia and transient thrombocytopenia, loss of appetite, distaste for food, pruritus vulvae, depression, dizziness, headache, leg cramps, lightheadedness, confusion, and fatigue. There is a small risk of ovarian cysts occurring. Hair thinning and/or hair loss has also been reported in women taking tamoxifen. Liver cancer and other liver toxicities such as fatty liver, cholestasis, hepatitis and hepatic necrosis have been reported in women taking tamoxifen, though such toxicities rarely can be severe or life-threatening. A few of these serious cases have resulted in death, but whether tamoxifen was the cause of these problems remains uncertain. An increased incidence of cataracts has been noted in rats, although such an increase has not been reported in humans. However, other ophthalmic toxicities, such as corneal scarring or retinal changes, have been reported in a few patients. Tumor flare can appear in patients being treated for metastatic disease. Tamoxifen should not be taken during pregnancy due to potential hazard to the fetus. This includes miscarriage, birth defects, or long-term effects on sexual development (which could be similar to the long-term effects caused by diethylstilbestrol [DES]). Women whose mothers took DES during pregnancy have an increased risk of developing cancer of the vagina or cervix, and may have trouble bearing children. The relevance of findings from animal studies to women who may accidentally take tamoxifen during pregnancy is unknown, but it is essential that effective contraceptive methods be used while taking tamoxifen therapy, and for two months after completing or discontinuing therapy. Tamoxifen may cause changes in the lining of the uterus which could potentially lead to uterine cancer. An early sign of abnormal changes in the uterus may be abnormal vaginal bleeding or pelvic discomfort. An increased risk of uterine cancer has been reported with the use of tamoxifen; however, the level of risk is still uncertain. After an average of 8 years of follow-up, the annual risk observed in a large-scale trial of breast cancer patients taking 20 mg of tamoxifen daily is about 2 per 1,000 women (approximately three times greater than that of a similar group of women in the general population.) Uterine cancer is potentially life-threatening, and some breast cancer patients who developed uterine cancer while taking tamoxifen have subsequently died from that disease. Most of the uterine cancers that have occurred have been diagnosed at an early stage when treatment is highly effective. Tamoxifen may cause changes in the lining of the uterus, such as polyps and hyperplasia, and endometriosis. Data from the NSABP B-14 study show no increase in other (non-uterine) cancers among patients receiving tamoxifen. However, other data suggest a possible increase in second cancers of the gastrointestinal tract among women receiving the drug. Whether an increased risk for other (non-uterine) cancers is associated with tamoxifen is still uncertain and will continue to be evaluated. Women on tamoxifen have an increased risk for developing phlebitis and blood clots. Some studies, but not all, have shown that tamoxifen causes about 1% increase in the incidence of thrombotic events. These include superficial phlebitis, deep vein thrombosis, and pulmonary embolism. Rarely, death has occurred from such events in these studies.

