Appendix 1 Study Calendar

Required studies	Baseline	After Randomization	Week 2 or 3	Day 29 (surgery day)	30 days post-surgery
HCG (serum or urine) Premenopausal women only	X				
H&P ¹	X				
Performance Status	X				
Blood for PK/PD studies (tamoxifen arm only)		X (2 green top)	X (1 green top)	X (1 green top)	
Adverse events assessment (tamoxifen arm only)		X	X	X	X
RPCI will be using DBBR Standard Banking Collection for DNA (Both observation arm and tamoxifen arm) University of Chicago will be collecting one EDTA (purple or pink) tube of blood for polymorphism studies	X(2)				
Core Bx for TAM and TAM metabolites levels, and future pharmacogenomic studies				X	
IHC for p53				X (3)	
ER/PR/HER-2 analysis	X			X	

1. **History and physical will include questions about prior history of thrombosis, stroke, and complete medication history. Gynecologic history will be obtained including LMP, history of dysfunctional bleeding, recent pap smears, and smoking history. Can use history and physical within 4 weeks prior to signing consent.**
2. **Patients need to consent to DBBR. DBBR sample must be collected prior to surgery. DBBR sampling will not be released until the end of study.**
3. **IHC for p53 will not be obtained until day of surgery**

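### Contraception is called essential during tamoxifen and for two months after, but the eligibility list and study calendar do not carry that condition, birth-control pills are barred without a stated replacement, and the pregnancy test has no window

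*Combined protocol and SAP*

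**What the plan says.** **The condition.** Section VIII, Clinical Safety and Adverse Effects, says "Tamoxifen should not be taken during pregnancy due to potential hazard to the fetus", names fetal harms, and then says "it is essential that effective contraceptive methods be used while taking tamoxifen therapy, and for two months after completing or discontinuing therapy".

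**Who can enter.** The Eligibility Criteria (under Study design, Section III) set no menopausal restriction: "The patient must be 18 years or older". Inclusion (h) asks for a negative "pregnancy test at screening for patients of child-bearing potential", and adds in brackets that "this is routinely done if the patient is premenopausal and having surgery". Exclusion (d) rules out "Pregnant or lactating women". Exclusion (f) rules out women receiving any hormonal therapy.

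**What is barred on study.** Section VII, Sex Hormonal Therapy: "Patients should not receive any sex hormonal therapy such as birth-control pills, hormone replacement therapy or infertility medications while on this protocol".

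**What is scheduled.** The Appendix 1 row "HCG (serum or urine) Premenopausal women only" has one mark, under Baseline, and no footnote giving a window.

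**The concern.** The protocol names a fetal hazard and the condition needed to control it, but the condition appears only in the descriptive drug section. Sites screen from the eligibility list and work from the calendar, and neither mentions contraception. The one rule that does touch it, in Section VII, removes a common method and is silent on what should replace it.

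The pregnancy test is the only operational safeguard. It is done once, its distance from the first dose is not bounded, and its target group has two descriptions.

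What is at stake is patient safety, not the primary comparison. A woman could stop the pill to enter, be allocated to tamoxifen, and satisfy every rule a monitor would check, without anyone having confirmed that the Section VIII condition is met.

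**Working it through.** No power, alpha or event figure is involved. The check is a reading of the relevant sections side by side, with simple day counts.

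**1. Is the condition carried into the operational text?**
- Inclusion (a) to (i): consent, age, histology, ER status, tumor size, planned surgery, performance status, pregnancy test, biobank consent. No contraception condition.
- Exclusion (a) to (n): current pregnancy or lactation under (d), hormonal therapy under (f). No contraception condition.
- Section IV and Appendix 1, footnote 1: the gynecologic history covers last menstrual period, dysfunctional bleeding, pap smears and smoking. Contraceptive method is not listed.
- Appendix 1: no contraception row.
- Result: in the supplied text, Section VIII is the only place that requires contraception.

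**2. How does Section VII interact with it?** Section VII bars hormonal methods such as the pill. Exclusion (f) bars hormonal therapy at entry, although its examples do not include the pill. Neither bars non-hormonal methods and neither requires one. Sections VII and VIII can therefore both be obeyed, but nothing checks that they are.

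**3. How long does the condition run?**
- Treatment: 28 days (Section IV).
- Two months: 59 to 62 days, depending on the calendar months.
- Total: 28 + 59 = 87 to 28 + 62 = 90 days.
- Final adverse event assessment: 30 ± 2 days after treatment completion (Section IX), so 28 to 32 days.
- Part of the condition falling after that assessment: 59 − 32 = 27 to 62 − 28 = 34 days.
- Appendix 1 counts the 30 days from surgery on day 29 instead, which shifts this by about one day.

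**4. When is the pregnancy test done?** Inclusion (h) places it at screening and Appendix 1 places it at Baseline, the column before randomization. The registration instructions for network sites (item 3) require eligibility to be determined before the registration form that triggers randomization is sent. The required test therefore precedes tamoxifen. What is missing is a limit on how long before:

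| Baseline item | Window stated |
|---|---|
| History and physical (Section IV, Appendix 1) | within 4 weeks before consent |
| Pre-dose blood for PK, hormones and genotyping (Section V, PK/PD studies) | 0 to 30 days before first dose |
| Pregnancy test (inclusion (h), Appendix 1) | none |

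**5. Who is tested?** Inclusion (h) refers to child-bearing potential and Appendix 1 to premenopausal women. Neither term is defined, and the two need not select the same women.

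**The case against.** Four points can fairly be made for the plan.

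**The sections do not conflict.** A reader might infer that barring the pill contradicts the call for contraception. It does not, because non-hormonal methods remain open. The bar also suits the design: Section III reports that estradiol strengthens the ERα-p53 interaction under study. Section VIII is itself protocol text, so a site that ignores it is not fully compliant. This stands, and it limits the point to a condition that is stated but not made operational.

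**The test comes before exposure.** Because inclusion (h) mentions routine testing before surgery, and surgery in the tamoxifen arm is on day 29, a reader might infer that the pregnancy test falls after the drug has been taken. The documents do not support that. The bracketed remark only says that such testing is routine; the required test is at screening. The missing window remains.

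**The consent form may cover it.** Those pages were not supplied, and signed consent is inclusion (a), so a contraception undertaking there would be tied to entry. This stands as a limit on the point. It does not alter the eligibility list, Section VII or the calendar, which still need to agree with Section VIII.

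**Few women may be affected.** Possibly. The documents give no menopausal breakdown, so no count can be defended in either direction.

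**Conclusion.** The point holds as a gap between the protocol's stated safety condition and its operational rules. The condition spans about 87 to 90 days, of which roughly 27 to 34 fall after the last scheduled adverse event assessment. Across that whole period the supplied eligibility list and calendar contain one pregnancy test, undated relative to the first dose, and no contraception requirement.

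This rests on two things: that the supplied criteria, Section VII and Appendix 1 are complete as printed, and that nothing is assumed about the consent pages.

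A reader might also infer that a pregnancy found on study would remove patients from the tamoxifen arm only and so bias the comparison. The supplied text has no off-study rule for pregnancy, so that should not be claimed. The issue is patient safety and consistency of the text. It merits correction but does not undermine the analysis.

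**What to change.** Reconcile the Eligibility Criteria, Section VII, Section VIII and Appendix 1 so that:

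- the eligibility list and calendar give effect to the condition that Section VIII calls essential, worded consistently with exclusion (f) and the Section VII bar on hormonal therapy;
- the timing of the already planned pregnancy test relative to the first tamoxifen dose is stated, and stated the same way in inclusion (h) and Appendix 1;
- the group to be tested is described by one defined term throughout.

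The consent form should be checked for agreement with the result. Which methods are acceptable, how long the window is and how the condition is worded are for the sponsor and investigators to decide.

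The cost is amendment wording. The planned pregnancy test stays. The possible downside is that a few women are not enrolled.

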Appendix 1 Study Calendar

Required studies	Baseline	After Randomization	Week 2 or 3	Day 29 (surgery day)	30 days post-surgery
HCG (serum or urine) Premenopausal women only	X				
H&P ¹	X				
Performance Status	X				
Blood for PK/PD studies (tamoxifen arm only)		X (2 green top)	X (1 green top)	X (1 green top)	
Adverse events assessment (tamoxifen arm only)		X	X	X	X
RPCI will be using DBBR Standard Banking Collection for DNA (Both observation arm and tamoxifen arm) University of Chicago will be collecting one EDTA (purple or pink) tube of blood for polymorphism studies	X(2)				
Core Bx for TAM and TAM metabolites levels, and future pharmacogenomic studies				X	
IHC for p53				X (3)	
ER/PR/HER-2 analysis	X			X	

1. **History and physical will include questions about prior history of thrombosis, stroke, and complete medication history. Gynecologic history will be obtained including LMP, history of dysfunctional bleeding, recent pap smears, and smoking history. Can use history and physical within 4 weeks prior to signing consent.**
2. **Patients need to consent to DBBR. DBBR sample must be collected prior to surgery. DBBR sampling will not be released until the end of study.**
3. **IHC for p53 will not be obtained until day of surgery**

2. INFORMED CONSENT

- Informed Consent must be obtained by the **Investigator** from any patients wishing to participate, **prior to any procedures or change in their treatment**
- An informed consent template is provided by RPCI and can be amended to reflect institutional requirements
- All consent changes **must** be reviewed by Roswell Park Cancer Institute Network Office prior to submission to the site IRB.
- The informed consent must be IRB approved
- Always check that you are using the correct date and version of the IRB approved consent.

3. PATIENT REGISTRATION AND RANDOMIZATION ASSIGNMENT

Phase II protocol registration instructions:

The **Subject Enrollment Log** must be faxed to the CRS Network Office within 24 hours of the date the patient is consented. Once the Principal Investigator has determined that eligibility has been met, complete the **Patient Registration Form** and **fax it** to the RPCI Network Office at [contact].

Note: The patient completes the **Gender, Race, and Ethnicity form** and this is placed in the study binder.

Roswell Park Cancer Institute does not grant exceptions to eligibility criteria.

Randomization Assignment:

Patients will be allocated to treatment or control by block randomization (block size=4). The randomization assignment list will be maintained at RPCI. The nurse/coordinator from University of Chicago will notify the RPCI Network office for a randomization assignment by sending the completed patient registration form to [contact]. The Network Monitor **or designee** will randomize the patient and send the randomization assignment to the nurse/coordinator at University of Chicago.

4. STUDY DEVIATIONS

- If a deviation has occurred to eliminate hazard, this should be reported to the RPCI Network, site IRB and any other regulatory authority involved in the trial.

- ANY study deviation will be recorded on the Study Deviation Log
- Patients who are inadvertently enrolled, with significant deviation(s) from the study-specified criteria, will be removed from the study
- Notify RPCI of any early patient withdrawal and appropriately document the discontinuation and the reason why.

5. STUDY DOCUMENTATION

- Study documents must be filled out completely and correctly. Ditto marks are not allowed.
- If an entry has been documented in error put a single line through the entry and initial and date the change. The auditor must be able to read what has been deleted.
 - Do NOT use white-out, magic marker, scratch-outs
 - Do NOT erase entries
- Use only black ink for documentation on the accountability form and any other study forms.

